5.7.4. Analysis of Vital Signs

Summaries of vital sign variables excluding measurements at each challenge level of DBPCFCs will include:

- Descriptive statistics of vital sign variables and change from baseline by visit
- Shift tables based on baseline normal/abnormal and other tabular and graphical methods may be used to present the results for parameters of interest

Summaries of vital sign variables (only systolic and diastolic blood pressure) at DBPCFCs of peanut protein at screening visit 1a, week 24 and week 36 will include:

• Descriptive statistics of vital sign variables (only systolic and diastolic blood pressue) and change from pre-dose by challenge dose level

Protocol: R668-ALG-1702

Date: March 3, 2021

• Shift tables based on baseline normal/abnormal and other tabular and graphical methods may be used to present the results for parameters of interest

The number (n) and percentage (%) of patients with treatment-emergent PCSV will be summarized. This summary will be provided based on all patients in the SAF as well as in the subgroup of SAF patients who did not meet the PCSV criterion at baseline.

Listings will be provided with flags indicating the treatment-emergent PCSVs and the status of impact by COVID-19 pandemic, depending on the data.

In addition, summaries of vital signs will be performed for patients who were impacted by COVID-19 pandemic and not impacted by COVID-19 pandemic, respectively. The summaries will be performed for pre-, during-, and post-COVID-19 period for patients impacted by COVID-19 pandemic, if applicable.

The graph of mean change and/or percent change from baseline value for vital sign parameters excluding measurements at DBPCFCs by visit will be provided.

5.7.5. Physical Exams

Shift tables based on baseline normal/abnormal status will be provided for assessments of each physical exam category and presented by visit. Only the physical examination on the second DBPCFC day at week 24 will be summarized in the shift table.

5.7.6. Spirometry and Peak Expiratory Flow (PEF)

Summaries of spirometry and PEF variables excluding measurement after DBPCFCs will include:

- Descriptive statistics of spirometry and PEF variables and change from baseline by visit will be presented
- Spaghetti plots of spirometry and PEF data will be displayed by visit

Summaries of spirometry and PEF variables for pre- and post-DBPCFCs of peanut protein will include:

- Descriptive statistics of spirometry and PEF variables and change from pre-dose will be presented
- Bar plots of spirometry and PEF data will be displayed

Summaries of spirometry and PEF variables for post-DBPCFCs of peanut protein by visit will include:

- Descriptive statistics of spirometry and PEF variables and change from post-DBPCFC of peanut protein at screening visit 1a by visit will be presented
- Bar plots of spirometry and PEF data will be displayed

Listing of spirometry and PEF data will be provided with flag indicating the status of impact by COVID-19 pandemic.

Protocol: R668-ALG-1702

Date: March 3, 2021

In addition, summaries of spirometry and PEF will be performed for patients who were impacted by COVID-19 pandemic and not impacted by COVID-19 pandemic, respectively. The summaries will be performed for pre-, during, and post-COVID-19 periods for patients impacted by COVID-19 pandemic, if applicable.

5.8. Analysis of Pharmacokinetic Data

The following analyses will be conducted:

- Descriptive statistics of functional dupilumab concentrations in serum at each sampling time by dose
- Graphical presentations of median and mean (+/- SD) functional dupilumab concentration in serum vs nominal time profiles
- Graphical presentations of individual functional dupilumab concentration in serum vs actual sampling time profiles

No formal statistical analysis will be performed. For the descriptive statistical analysis, concentrations below the lower limit of quantitation (LLOQ) will be set to zero. When plotted on semi-log scale, concentrations are imputed as LLOQ/2. Mean data are presented by nominal time. Individual concentrations are presented by actual time.

5.9. Analysis of Immunogenicity Data

5.9.1. Analysis of ADA Data

The immunogenicity variables described in Section 4.8 will be summarized using descriptive statistics. Immunogenicity will be characterized by ADA responses and titers observed in patients in the ADA analysis set.

The following will be summarized by treatment group and ADA titer level:

- Number (n) and percent (%) of ADA-negative subjects (pre-existing immunoreactivity or negative in the dupilumab ADA assay at all time points)
- Number (n) and percent (%) of treatment-emergent ADA-positive patients
 - Number (n) and percent (%) of persistent treatment-emergent ADA positive patients
 - Number (n) and percent (%) of indeterminate treatment-emergent ADA positive patients
 - Number (n) and percent (%) of transient treatment-emergent ADA positive patients
- Number (n) and percent (%) of treatment-boosted ADA-positive patients

Listing of all ADA titer levels will be provided for patients with pre-existing, treatment-emergent and treatment-boosted ADA response.

5.9.2. Analysis of Neutralizing Antibodies (NAb) Data

The absolute occurrence (n) and percent of patients (%) with NAb positive or negative status will be provided by treatment group for patients in the NAb analysis set.

Protocol: R668-ALG-1702

Date: March 3, 2021

5.10. Association of Immunogenicity with Exposure, Safety and Efficacy

5.10.1. Immunogenicity and Exposure

Potential associations between immunogenicity variables and systemic exposure to dupilumab will be explored. Plots of individual dupilumab concentration may be provided for analyzing the potential impact of treatment-emergent ADA responses, titer (high, moderate or low) and NAb on PK profiles.

5.10.2. Immunogenicity and Safety and Efficacy

Potential association between immunogenicity variables and safety may be explored with a primary focus on the following safety events during the TEAE period:

- Injection site reaction (serious or severe and lasting 24 hours or longer)
- Hypersensitivity (SMQ: Hypersensitivity [Narrow])
- Anaphylaxis (SMQ: Anaphylaxis [Narrow])

Potential association between immunogenicity variables and primary efficacy endpoints may be explored (e.g. scatter plot or spaghetti plot).

The safety and efficacy analyses mentioned above will be conducted using the following ADA response categories:

- ADA positive patients, that is patients with treatment-emergent or treatment-boosted response
- ADA negative patients, that is patients with pre-existing immunoreactivity or negative in the ADA assay at all time points
- Patients with persistent treatment-emergent ADA response
- NAb positive patients, that is patients who were positive in the NAb assay at any time point analyzed

• Maximum post-baseline titer level in treatment-emergent or treatment boosted ADA positive patients:

Protocol: R668-ALG-1702

Date: March 3, 2021

- High,
- Moderate,
- Low

5.11. Analysis of Biomarker Data

All biomarker analyses will be performed on the SAF using all observed data. Descriptive statistics for the observed values, change from baseline and percent change from baseline values by visit will be provided for the biomarker variables as described in Section 4.9.

The Wilcoxon signed-rank test will be used to test if the change or percent change from baseline value is significantly different from zero. P-value will be reported.

Correlation of baseline biomarkers [including serum peanut sIgE, sIgG, sIgG4, total IgE, and basophil sensitivity to peanut allergen stimulation measured by EC50, frequency of peanut specific T-cell subsets (e.g. Th2A cells)], absolute change or percent change at week 24 and 36 from baseline in these biomarkers with the following continuous clinical endpoint will be explored using Spearman's rho test. Both Spearman correlation coefficients and p-value will be reported. The correlation between post-baseline biomarkers and clinical outcome will only be evaluated at the same visit.

• Change in the cumulative tolerated dose (log transformed) mg of peanut protein during a DBPCFC from baseline to measured DBPCFC visits at weeks 24 and 36

Correlation of baseline biomarkers [including serum peanut sIgE, sIgG, sIgG4, total IgE, and basophil sensitivity to peanut allergen stimulation measured by EC50, frequency of peanut specific T-cell subsets (e.g. Th2A cells)] with the following binary clinical endpoints will also be explored using logistic model. The model will include the responder/non-responder of below clinical endpoint as the dependent variable and baseline biomarker as the predictor variable. Model coefficients and p-value will be provided to indicate significance of the correlation/association.

• Proportion of patients treated with dupilumab that pass a DBPCFC with at least 444 mg (cumulative) peanut protein at week 24

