Dupilumab, a fully human VelocImmune[®]-derived monoclonal antibody directed against interleukin-4 receptor alpha (IL-4R α), blocks the activity of IL-4 and IL-13 and is approved as a treatment for atopic dermatitis (AD). As of October 2019, dupilumab has been approved for the adult atopic dermatitis (AD) indication in over 40 countries worldwide. Additionally, dupilumab has been approved for severe asthma with type 2 inflammation in both adult and adolescent patients, and recently in adult patients with chronic rhinosinusitis with nasal polyposis (CRSwNP), and adolescents with AD. Dupilumab is also under development for a range of type 2 inflammatory diseases such as food allergies and eosinophilic esophagitis (EOE) amongst others.

This phase 2 proof-of-concept (POC) study will explore whether dupilumab has immunomodulatory effects on Type 2 immune responses, which may result in improved safety and tolerance to peanut exposure as determined by the ability to tolerate a higher cumulative peanut protein dose level during a double-blind, placebo-controlled food challenge (DBPCFC) after 24 weeks of monotherapy treatment. In addition, the study will evaluate whether dupilumab influences known biomarkers important in the allergic response to peanuts such as a reduction in allergen-specific IgE and/or increase in allergen-specific IgG4.

Additional background information on the study drug and development program can be found in the Investigator's Brochure.

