4.5.2. Secondary Efficacy Variable(s)

The secondary efficacy endpoints include:

- Change in the cumulative tolerated dose (log transformed) mg of peanut protein during a DBPCFC from baseline to measured DBPCFC visits at weeks 24 and 36
- Proportion of patients treated with dupilumab that pass a DBPCFC with at least 444 mg (cumulative) peanut protein at week 36
- Proportion of patients treated with dupilumab that pass a DBPCFC with at least 1044 mg (cumulative) peanut protein at weeks 24 and 36
- Proportion of patients treated with dupilumab that pass a DBPCFC with at least 2044 mg (cumulative) peanut protein at weeks 24 and 36
- Percent change from baseline in sIgE to post-baseline visits (weeks 4, 8, 12, 24, and 36)

• Change from baseline in titrated SPT at week 4, 12, 24, 36 as measured by the average wheal size AUC after peanut allergen stimulation at different concentrations

Protocol: R668-ALG-1702

Date: March 3, 2021

- Proportion of patients with Grade II or above allergic reactions during the DBPCFC at week 24
- Proportion of patients using epinephrine as a rescue medication during the DBPCFC at week 24

Titrated Skin Prick Test (SPT)

The titrated SPT is the skin testing for atopic response at different concentrations of peanut extract with saline as negative control and histamine as positive controls. The SPTs will be performed starting at the following dilutions: neat, 1:20, 1:200, 1:2,000, 1:20,000. Wheal size induced by peanut extract at each concentration will be calculated as the average of the largest diameter and the perpendicular midpoint diameter.

The formula used to calculate the average wheal diameter at each concentration described in Section 6.3.

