4.9. Pharmacodynamic and Biomarker Variables

Pharmacodynamic and biomarker variables are:

- Serum TARC and total IgE
- Peanut-specific IgE, IgG, IgG4
- Titrated Skin Prick Test
- Fractional Exhaled Nitric Oxide (FeNO)
- Basophil sensitivity to peanut allergen (EC50)
- Frequency of peanut specific Th2A cells

Biomarker samples will be collected at time points according to according to Section 10.2.

Protocol: R668-ALG-1702

Date: March 3, 2021

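### SAP 5.11 leaves the biomarker signed-rank test on absolute or percent change; on the percent scale it leans towards false increases and loses power for modest decreases

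*SAP*

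**What the plan says.** SAP 5.11 covers the markers listed in SAP 4.9: "Serum TARC and total IgE"; "Peanut-specific IgE, IgG, IgG4"; the titrated skin prick test (SPT); FeNO; basophil EC50; and the frequency of peanut-specific Th2A cells. For these it says: "The Wilcoxon signed-rank test will be used to test if the change or percent change from baseline value is significantly different from zero". It continues: "P-value will be reported". On the data used: "All biomarker analyses will be performed on the SAF using all observed data".

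The section does not assign a scale to each marker, say which p-value governs if the two scales disagree, or give a significance level or sidedness. It mentions neither a log ratio nor the symmetry assumption.

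Three other places bear on the point:

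- SAP 4.5.2 lists a percent-scale secondary endpoint: "Percent change from baseline in sIgE to post-baseline visits (weeks 4, 8, 12, 24, and 36").
- SAP 4.5.3 lists absolute change for peanut-specific IgE (sIgE), and both scales for IgG, IgG4, the antibody ratios, EC50 and T-cell subsets.
- Protocol Section 1 names the biomarker effects of interest: "such as a reduction in allergen-specific IgE and/or increase in allergen-specific IgG4".

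**The concern.** The signed-rank test gets its null distribution by flipping the sign of each value at random. It therefore tests symmetry about zero, not only a zero median. For absolute change the two agree if baseline and follow-up are exchangeable. For percent change they do not. If post/baseline is symmetric on the log scale, percent change has median zero but is bounded at −100% below and unbounded above. Rises then take the larger ranks.

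The error has a direction. It helps a marker that is hoped to rise, such as IgG4, and hinders one that is hoped to fall, such as sIgE. There is no control arm against which such a bias would cancel. Because SAP 1.2.3 removes p-values from the primary and secondary endpoint analyses, the tests in 5.11 are the only change-from-baseline p-values the SAP says it will report.

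**Working it through.** **The plan's own figure.** The documents size only the primary endpoint (SAP 2.3). With p0 = 0.08, p1 = 0.29, two-sided 5% and 80% power:

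n = ((1.96·√(0.08·0.92) + 0.842·√(0.29·0.71)) / 0.21)² = 18.93, rounded up to 19, against the stated 20.

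Power at n=20 is 81.5%, and 20/0.85 = 23.5, rounded up to 24. The figure is reproduced closely. It supplies the two sample sizes used below, 20 and 24. No size or power is stated for the biomarker tests.

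**The mechanism in four patients.** Take post/baseline ratios 0.5, 2, 0.8 and 1.25, which balance exactly on the log scale.

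- Log ratios are ±0.693 and ±0.223. The tied ranks are 1.5, 1.5, 3.5, 3.5, so the positive and negative rank sums are both 5.
- Percent changes are −50, +100, −20 and +25. Ordered by size (20, 25, 50, 100), the positive rank sum is 2 + 4 = 6 and the negative is 1 + 3 = 4.

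The imbalance comes from the scale alone.

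**Simulation inputs.** Log(post/baseline) is Normal(log ratio, SD); exact signed-rank critical values, two-sided 5% (assumed, since 5.11 is silent). The within-patient log SD is not in the documents and is varied. For scale, with no effect, 95% of ratios lie within exp(±1.96·SD): about 0.68 to 1.48 at SD 0.2, and 0.14 to 7.1 at SD 1.0.

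**No true change, n=24, percent change** (exact level about 2.4% each way):

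| Log SD | False increase | False decrease |
|---|---|---|
| 0.2 | 3.8% | 1.5% |
| 0.5 | 6.6% | 0.9% |
| 1.0 | 12.4% | 0.4% |

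The log ratio stays near 2.4% each way. So does absolute change when visits are exchangeable. At n=20 the percent-change pattern is the same: 3.4%/1.7%, 5.9%/1.0% and 10.7%/0.6% at the same SDs. At SD 0.1 it is 2.9%/2.0%.

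**Power to detect a fall, percent change against log ratio:**

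| True fall | n | Log SD | Percent change | Log ratio |
|---|---|---|---|---|
| 20% | 24 | 0.5 | 33% | 53% |
| 30% | 24 | 0.6 | 54% | 78% |
| 30% | 24 | 0.8 | 25% | 53% |
| 50% | 20 | 0.5 | 99.8% | 100% |
| 50% | 20 | 0.7 | 90% | 98% |
| 50% | 20 | 1.0 | 50% | 82% |

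The mirror-image rise gains what the fall loses. For a ratio of 1.25 at n=20 and SD 0.5, power is 62% on percent change against 46% on the log ratio.

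**The case against.** The strongest reply is about scope and stakes, and most of it stands.

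- **Only one of two named scales is affected.** A reader might infer that every test in 5.11 is biased. The text does not support that: absolute change is also allowed, and it keeps its level when visits are exchangeable.
- **Decreases would not generally be missed.** A reader might infer that falls in sIgE, TARC or FeNO would go undetected. The only expected size of fall in the documents is about 50%, for total IgE (Protocol 5.6 and 9.2.6.2). There the percent scale still has about 90% power or more up to SD 0.7. The 20% and 30% falls above are illustrations, not figures from the plan.
- **The size rests on an assumed SD.** At SD 0.2 or below, the total error is close to 5%. What remains is the imbalance between directions: 3.8% against 1.5% at n=24.
- **The p-values are supportive.** A reader might infer that the mechanism claim rests on them. No decision rule attaches to 5.11. Protocol 11.4.7 summarises exploratory biomarkers descriptively, and SAP 5.6.2 treats all secondary endpoints descriptively, so the sIgE p-value sits beside its endpoint analysis.
- **Favourable directions are only partly documented.** The documents support sIgE falling and IgG4 rising. The IgG rise in Protocol 5.6 is described for oral immunotherapy, and no direction is stated for EC50 or Th2A cells. A general claim of false positives favouring dupilumab would go too far.

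One further defence is that the mean percent change really is above zero: for a lognormal ratio with no effect it is exp(SD²/2) − 1, or 13% at SD 0.5. But that excess is produced by variability alone, so rejecting because of it says nothing about a drug effect.

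The reply does not remove the defect on the percent scale, or the absence of a rule that picks one scale per marker.

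**Conclusion.** The concern holds for the percent-change option. With no effect at n=24, the false-increase rate is about 4% to 12% and the false-decrease rate about 1.5% to 0.4%, against about 2.4% each, for log SD 0.2 to 1.0. Power is lost for modest falls or noisy markers, and little is lost for a fall near 50% with SD up to 0.7. The open choice of scale adds to the problem, since two p-values for one marker can disagree.

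These figures assume a normal log ratio, a two-sided 5% level, 20 or 24 evaluable patients and an SD range the documents do not supply. The direction of the bias follows from the skewness of percent change; its practical size depends on the SD. The primary endpoint is unaffected. This is a worthwhile correction to supportive analyses and does not threaten the trial's main result.

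**What to change.** Replace the test sentence in SAP 5.11 with a rule that fixes one scale per marker:

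- For TARC, total IgE, peanut-specific IgE, IgG and IgG4, FeNO and EC50, apply the signed-rank test to log(post-baseline/baseline). Back-transform the estimate and 95% confidence interval and present them as percent change.
- For titrated SPT AUC and Th2A frequency, which can be zero, apply the test to absolute change.
- Keep percent change as a descriptive summary, without a p-value.

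The log is workable for the first group because SAP 6.2 already sets biomarker values below the quantification limit to half that limit. The cost is a short SAP edit and a log transform in the program. The small downside is that the marker set is then tested on two scales.

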6. DATA CONVENTIONS

The following analysis conventions will be used in the statistical analysis.

6.1. Definition of Baseline for Efficacy/Safety Variables

Unless otherwise specified, the baseline assessment for all measurements will be the latest available valid measurement taken prior to the administration of investigational product. The following rules specify the determination of baseline by both date/time information:

• The date and time of first injection will be used to determine the baseline for the AE, lab, PK and ADA data.

Protocol: R668-ALG-1702

Date: March 3, 2021

• Only the date of first injection will be used to determine the baseline for other data except the AE, lab, PK and ADA data.

6.2. General Data Handling Conventions

For the laboratory safety variables and biomarker data, if the data are below the lower limit of quantification (LLOQ)/limit of linearity, half the lower limit value (i.e., LLOQ/2) will be used for quantitative analyses. For data above the upper limit of quantification (ULOQ)/ limit of linearity, the upper limit value (i.e., ULOQ) will be used for quantitative analyses.

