5.6. Pharmacodynamic and Biomarker Variables

Serum TARC and Total IgE. Serum TARC and total IgE are markers of Type 2 activity. Dupilumab significantly suppressed both TARC and total IgE in studies of adult AD, nasal polyposis, and asthma patients.

Peanut-specific IgE, IgG, IgG4. The induction of peanut-specific IgG4 and IgG during OIT has been reported in multiple studies, and is thought to have a protective effect against IgE-mediated allergic symptoms. The gradual increase in serum allergen-specific IgG4, and decrease in allergen-specific IgEs are associated with clinical desensitization to peanut ([Glaumann, 2015](#)). In a 5-year peanut OIT study of 39 peanut-allergic children, increases in total peanut-specific IgG levels were reported during the 12-month up-dosing period ([Vickery, 2014](#)). In an open-label study of 29 peanut-allergic children, peanut-specific IgG4 increased steadily during the first year of treatment, reaching 3.5-fold increase over baseline after 3 months of OIT and roughly 10-fold increase at the end of first year ([Jones, 2009](#)). In the same study, peanut-specific IgE increased by ~3 fold after 3 months of OIT and gradually returned to baseline at one year. In a study investigating the biomarker profile of dupilumab in patients with AD (R668-AD-1307 as well as other dupilumab studies), dupilumab suppressed both total and allergen-specific IgEs. In general, dupilumab suppresses total serum IgE by ~ 50% with 12 to 16 weeks of treatment.

Titration Skin Prick Test. The titrated SPT will assess the atopic response to peanut extract. A statistically significant reduction in wheal size has been associated with clinical desensitization for peanut allergy in a randomized controlled study of peanut OIT for 12 months ([Varshney, 2011](#)).

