7.2.1. Inclusion Criteria

A patient must meet the following criteria to be eligible for inclusion in the study:

1. Age 6 to 17 years (inclusive).
2. Patient has a clinical history of allergy to peanuts or peanut-containing foods (symptom[s] of reaction due to exposure).
3. Experience dose-limiting symptoms at or before the 100 mg challenge dose (≤ 144 mg cumulative) of peanut protein (measured as 200 mg of peanut flour) on screening DBPCFC conducted in accordance with PRACTALL (Practical Issues in Allergology, Joint United States/European Union Initiative) guidelines. And not experiencing dose limiting symptoms to placebo
4. Serum IgE to peanut of ≥ 10 kUA/L and/or a SPT to peanut ≥ 8 mm compared to a negative control.

5. Patients/legal guardians must be trained on the proper use of the epinephrine autoinjector device to be allowed to enroll in the study.
6. Patients with other known food allergies must agree to eliminate these other food items from their diet so as not to confound the safety and efficacy data from the study.
7. Written informed consent from parent/guardian.
8. Written assent from minor patients as appropriate (eg, above the age of 6 years or the applicable age per local regulatory requirements).
9. Willing and able to comply with all clinic visits and study-related procedures.

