3.4. Subgroups

Subgroups are defined by key baseline factors recorded on the eCRF (unless otherwise specified) and listed as follows.

Subgroups to be considered for both efficacy and safety analyses:

- Age group (>=6 to <12 years, >=12 to <=17 years)
- Sex (Male, Female)
- Screening peanut-specific IgE level (≤100 kUA/L, >100 kUA/L)
- Baseline body weight ($\geq 20 \text{ kg}$ and $\leq 60 \text{ kg}$, $\geq 60 \text{ kg}$)

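### Setting peanut sIgE values above the assay's upper limit equal to that limit can understate the fall in sIgE, if any baselines exceed the limit; the plan gives neither the limit nor a check.

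*SAP*

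**What the plan says.** - **The rule.** SAP 6.2 (General Data Handling Conventions) sets its scope in the opening words: "For the laboratory safety variables and biomarker data, if the data are below the lower limit of quantification (LLOQ)/limit of linearity". Half the lower limit is then used. The next sentence deals with results above the upper limit or limit of linearity: "the upper limit value (i.e., ULOQ) will be used for quantitative analyses".
- **Its reach.** SAP 4.9 lists "Peanut-specific IgE, IgG, IgG4" among the pharmacodynamic and biomarker variables, so the rule applies to sIgE.
- **The endpoint.** SAP 4.5.2 includes among the secondary efficacy variables "Percent change from baseline in sIgE to post-baseline visits (weeks 4, 8, 12, 24, and 36".
- **The analysis.** SAP 5.11 summarises observed values, change and percent change by visit. It adds: "The Wilcoxon signed-rank test will be used to test if the change or percent change from baseline value is significantly different from zero". It also correlates baseline sIgE, and its change at weeks 24 and 36, with the change in log cumulative tolerated dose. SAP 4.5.3 adds the sIgG4/sIgE and sIgG/sIgE ratios as exploratory variables.
- **Expected values.** Protocol 7.2.1 sets a floor but no ceiling: "Serum IgE to peanut of ≥ 10 kUA/L and/or a SPT to peanut ≥ 8 mm compared to a negative control". SAP 3.4 defines a subgroup by "Screening peanut-specific IgE level (≤100 kUA/L, >100 kUA/L".
- **What is absent.** Neither document gives the sIgE assay's upper limit, says whether over-range samples are diluted and re-read, or plans a sensitivity analysis for capped values. The efficacy table in SAP 10.1 has no row for sIgE.

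**The concern.** A result above the limit is right-censored: the true value is at least the limit. Substituting the limit is harmless in many summaries but not in a ratio to baseline. If the baseline is capped, the denominator is too small and a fall looks smaller than it was. If both visits are capped, the recorded change is exactly 0% whatever happened.

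At stake is the reading of a secondary endpoint tied to a stated secondary objective, the effect on peanut-specific IgE. Three other analyses use the same capped values. In the signed-rank test, forced zeros carry no information. The two ratios take the distorted sIgE as denominator. In the Spearman correlations, capped baselines become ties and the ranks of the changes shift. With about 24 patients, a handful of forced zeros matters, and a reader of the output could not tell a true non-response from a capped one.

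**Working it through.** The plan states no figure for the ULOQ, the share of patients above it or the expected sIgE change, so there is no planned figure to reproduce on this point.

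**Step 1: one patient.** Let B be the true baseline, F the true follow-up value and U the ULOQ. The true change is F/B - 1; the recorded change is min(F,U)/min(B,U) - 1. Write k = B/U and let R be the true fall, so F = (1 - R)B. For k above 1 the recorded change is min((1 - R)k, 1) - 1. With R = 0.5:
- k ≤ 1: no capping, -50%
- k = 1.2: 0.60 - 1 = -40%
- k = 1.5: 0.75 - 1 = -25%
- k ≥ 2: 1 - 1 = 0%

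At k = 1.5, a true 30% fall reads 0% and a true 70% fall reads -55%. Capping never moves a patient's percent change away from zero; in simulation no patient's did. It would hide a rise in the same way.

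**Step 2: the group, relative to the limit.** Assumptions: lognormal baselines (log SD 1.0 or 1.5), true 50% fall, follow-up log-noise SD 0.2. The true mean is -49% and the true median -50%.

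| Baselines above ULOQ | Capped mean | Capped median |
|---|---|---|
| 1% | -48.8% | -49.9% |
| 21-24% | about -42% | about -47% |
| 50% | -30% to -32% | -37% to -39% |
| 73-82% | -15% to -18% | 0% |

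With half the baselines above the limit, true means of -29% and -69% (true falls of 30% and 70%) become -16% to -17% and -47% to -52%.

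**Step 3: the group, in kUA/L.** Assumptions: baseline lognormal with median 40, 80 or 150 kUA/L and geometric SD 2.5 or 4; post/baseline ratio lognormal with median 0.5 and log SD 0.4. The -50% borrows the statement in Protocol 5.6 that "dupilumab suppresses total serum IgE by ~ 50% with 12 to 16 weeks of treatment"; that section says allergen-specific IgE also falls but gives no size.

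| Assumed ULOQ (kUA/L) | Reported median (true -50%) |
|---|---|
| 100 | -16% to -47% |
| 200 | -37% to -49% |
| 500 | -46% to -50% |
| 1000 | -48% to -50% |

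At ULOQ 100, 16% to 67% of baselines are capped. The ends follow from ln(100/40)/ln 2.5 = 1.00, upper tail 16%, and ln(100/150)/ln 2.5 = -0.44, upper tail 67%. Of 24 patients that is about 4 to 16. Between 5% and 42% of patients record exactly 0%.

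**Step 4: the possible remedies, at ULOQ 100.**
- Restricting to patients with baseline below the ULOQ recovers -50%, because the simulation makes response independent of baseline.
- A bivariate model with log sIgE at each visit right-censored at log ULOQ gives -50% to -51%, under the same independence.
- A univariate censored-normal model of log(post/baseline) does not work. A capped baseline left-censors the ratio, and two capped values leave it unidentified. With the censoring direction set correctly it gives -51% to -57%. Treating every capped pair as right-censored gives -45% to +24%, worse than capping in every scenario.

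**The case against.** The strongest reply is that nothing in the documents shows any patient above the limit. If the laboratory dilutes over-range samples and reports a measured value, the rule never applies and the bias is nil. The size rests on assumed baselines, assumed limits and a total-IgE figure used as a proxy. It runs from negligible to severe, with nothing in the documents to choose between the two. This stands, and it makes the conclusion conditional.

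A reader might infer three stronger things:
- **That the endpoint does understate the drug effect.** This needs baselines above the ULOQ and a true fall. The protocol expects a fall, but the documents do not establish the first condition.
- **That 100 kUA/L is the assay limit, because SAP 3.4 cuts there.** The cut shows only that values above 100 are expected. They may be fully quantified.
- **That the plan would report a false difference in sIgE response by baseline level.** SAP 5.6.5 confines efficacy subgroups to the primary endpoint and three challenge endpoints, so no such comparison is planned. The artefact could arise only in a post hoc comparison or through the correlations.

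It is also fair to say that this is a single-arm proof-of-concept study with largely descriptive analyses, that the ratios are exploratory, and that the median, already standard output under SAP 5 and 5.11, moves less than the mean until many values are capped. None of this removes the problem. The capping rule is explicit, its direction is fixed by arithmetic, SAP 5.11 still reports a p-value, and the plan has no check on the rule's effect.

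**Conclusion.** The concern holds as a conditional statement. SAP 6.2 applies a capping rule to a secondary percent-change endpoint. For any patient whose baseline exceeds the ULOQ, it can only shrink the recorded change, to exactly zero if both values are above the limit. If sIgE falls on treatment and some baselines exceed the limit, the endpoint understates the fall.

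The group-level size is known only as a range. For an assumed true median of -50%, it runs from a 3 to 34 percentage-point understatement at ULOQ 100 (50 - 47 and 50 - 16) to at most 2 points at ULOQ 1000 (50 - 48). It is nil if over-range samples are diluted and quantified. The primary endpoint and the sample size are not affected.

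**What to change.** In the SAP, for sIgE and likewise sIgG and sIgG4:
1. Use the diluted, quantified result wherever the laboratory reports one, and apply the cap only where none exists.
2. State the assay limit.
3. Report the number of values at the ULOQ at baseline and at each visit.
4. Repeat the percent-change summary and the Wilcoxon test in patients whose baseline is below the ULOQ, noting that this represents the whole group only if response does not depend on baseline level.

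If a model is wanted, treat log sIgE at each visit as right-censored at log ULOQ in a joint (bivariate or mixed) model, and report the geometric mean ratio with a 95% confidence interval. Do not fit a right-censored model to log(post/baseline).

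The cost is SAP wording and one extra table based on fewer patients; no new samples are needed. If the limit proves high, the results will change little and the count of capped values will show why.
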